## 9.2. Hypothesis Testing

The purpose of this study is to determine if the effectiveness of cetirizine 10 mg/mL injection is non-inferior to the effectiveness of diphenhydramine 50 mg/mL. The non-inferiority margin will be set at **CCI**. See [Section 5](#) for the rationale.

The null hypothesis is that cetirizine is inferior to diphenhydramine if the difference is **CCI** with 95% confidence. The null hypothesis is stated as:

$$H_0: \text{CCI} \leq \text{CCI}$$

where D2 is the change from baseline of the 2 hr patient rated severity of pruritus for each treatment. The alternative hypothesis to be tested is:

$$H_1: \text{CCI} > \text{CCI}$$

If the null hypothesis is rejected in favor of the alternative (e.g., cetirizine is not inferior to diphenhydramine) and if the treatment difference **CCI** then the alternative

---

hypothesis will be further refined in a stepwise manner to test for superiority of cetirizine over diphenhydramine:

H2: **CCI** **CCI**

This stepwise process of testing for superiority only after rejecting the null for non-inferiority will spare type I error. Details of the methods to be used are provided in [Section 10.1](#),

### **9.3. Adjustments for Multiplicity**

There is only one primary endpoint being tested to determine efficacy of cetirizine 10 mg/mL injection on 2hr patient rated pruritus severity. Key secondary endpoints will be used to support the claims of the primary efficacy outcome. There are 2 outcome measures that are key in supporting the efficacy claim: the need to return to treatment center after study discharge and time spent at the treatment center (time from treatment administration to readiness for discharge). Family-wise error rate will be controlled using Holm-Bonferroni method of rejecting individual hypotheses ([Holm, 1979](#)).

Although nominal p-values will be reported for treatment differences, none of the other secondary endpoints will be used to evaluate for superiority or non-inferiority of cetirizine compared to diphenhydramine, therefore no adjustments for multiplicity are planned.

### **9.4. Covariates**

No covariates are planned. However, in the event there are some treatment disparities in baseline characteristics (e.g., age or weight), covariates may be added to the analysis of the primary endpoint as part of the per protocol analysis.

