### 9.1. Imputed and Missing Data

The primary efficacy analysis will be performed on the ITT population. Subjects may be discharged at any time after 1 hr post-treatment assessment, which would result in missing data at the 2 hr post-treatment assessment time. Therefore, assessments of pruritus, extent of urticaria, and sedation for subjects discharged prior to the 2 hr assessment will be carried forward from the last recorded score to 2 hrs and beyond.

In addition, subjects may receive rescue medication at any time post-study drug and prior to Readiness for Discharge if the attending physician deems it necessary. Any assessment of pruritus, extent of urticaria and sedation after administering rescue medication will be confounded with the response to rescue medication. If a subject is given one or more rescue medications prior to the 2 hr assessment, the last pre-rescue assessments will be carried forward to the 2 hr assessment and to any post-rescue assessments.

Since the use of rescue would always occur prior to readiness for discharge, the use of rescue will always supersede early discharge with regards to carrying the last observation forward. As long as rescue drug

---

is used, the pre-rescue score will be carried forward to all subsequent assessment including the 1hr, 2hr, and readiness-for-discharge-assessment.

Examples:

- i) If the earliest rescue is used at 30 minutes after study drug, and the patient's readiness-for-discharge is at 1.5hr, the baseline scores (the last pre-rescue score) will be carried forward to the 1hr, 2hr and discharge assessments, regardless of the existing assessments at 1hr and 1.5hr (the discharge assessment).
- ii) If the earliest rescue is used at 30 minutes after study drug, and the patient is ready for discharge at 2.5hr post study drug, the baseline scores (the last pre-rescue-score) will be carried forward to the 1hr, 2hr and discharge assessments, regardless of the existing assessments at 1hr, 2hr and 2.5hr (the discharge assessment).
- iii) If the earliest rescue is used at 3hrs after study drug, and the patient's readiness-for-discharge is at 4hrs, the 2hr scores (the last pre-rescue-scores) will be carried forward to the discharge assessment regardless the existing 4hr assessment (the discharge assessment).
- iv) For a patient without rescue drug, if readiness-for-discharge occurs at 1.5hr, the discharge assessment (1.5hr, the last obtained score) will be carried forward to 2hr.

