### **9.7. Study Centers**

A total of 22 study centers will be used in this protocol. The likelihood that all centers enroll an equal number of subjects is small. No center will be allowed to enroll more than 20% of the entire study population (N=87). In the event there is a discrepancy of more than 10% between the largest enrolling center and smallest, centers will be pooled from the ranked extremes until the pooled centers are within of each other (e.g. the smallest center will be pooled with the largest, and so forth). Study centers will be added to the analysis of variance model for the primary endpoint. See [Section 10.1](#) for details of methods.

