**9.11. Changes from Protocol Planned Analysis**

The protocol included collecting information on the reason for use of rescue drugs (secondary objective #7), however, it was determined at the time of CRF development that capturing such data would not add to the determination that a rescue medication was given. Therefore, this was not captured.

The sample size justification in the protocol was not updated to match the final methodology used. While both the protocol and the SAP sample size justifications results in the need for 127 subjects per treatment arm, the assumptions in this SAP are more indicative of the actual assumptions and methodology used to arrive at this sample size.

The protocol did not make provisions for subjects who needed to be hospitalized or kept in the ED overnight for observations. The SAP covers the needs to treat the time spent at the treatment center to “missing” for these subjects.

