**10.2. Protocol Deviations**

All randomized subjects will be included in the ITT and SAF populations. If a violation hinders the ability to assess an efficacy outcome, the following approaches can be taken:

Examples:

- i) If patient does not have the disease intended to treat, the outcome for the 2 hr assessment will be set to the baseline values and the subjects will be considered a treatment failure. In this example, the “readiness for discharge” time will be missing, since the discharge time is confounded by the wrong disease.
- ii) if a subject receives an antihistamine within 2 hrs prior to baseline (not meeting exclusion #4), that subject will be considered a failure with change from baseline to 2 hr pruritus score and with change from baseline to 2 hr extent of urticaria score set to zero (0). In this example, sedation score will be missing since sedation is confounded by the antihistamine prior to baseline.

---

Inclusion of subjects in other efficacy endpoints will be dependent on availability of data for each assessment times point. Subject data will be reviewed for major protocol violations by a qualified clinical reviewer prior to database lock and unblinding. Subjects with any major protocol violations will be identified and excluded from the Per Protocol Population. A summary list of the individual subjects excluded, will be provided, sorted by treatment group with description of their protocol violation/deviation.

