## 11. EFFICACY ANALYSES

### 11.1. Primary Endpoint

The primary clinical outcome measure is patient rated severity of pruritus at 2 hr post-treatment. The primary analysis will test for the non-inferiority of cetirizine to the active comparator, diphenhydramine, for the mean change from baseline in patient rated pruritus at 2 hours. See [Section 9.9](#) for derivation of this endpoint. Using the notation of [Gupta, 2011](#), the NI margin of -0.50 will be used to test the hypothesis:

$$H_0: \text{CCI} \quad \text{CCI}$$

---

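### The primary ITT analysis of D2 has no visible adjustment for baseline pruritus, and the only covariate option is triggered by imbalance and confined to the per-protocol set

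*SAP*

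**What the plan says.** SAP 9.4 opens with "No covariates are planned". It then makes one exception: if the arms differ on baseline characteristics, with age and weight given as examples, "covariates may be added to the analysis of the primary endpoint as part of the per protocol analysis".

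The other relevant places are:

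- **Population.** SAP 9.1: "The primary efficacy analysis will be performed on the ITT population".
- **Endpoint.** SAP 9.2 and 11.1 use D2, the change from baseline to 2 hours in patient-rated pruritus. In 11.1, "the NI margin of -0.50 will be used to test the hypothesis".
- **Model.** SAP 9.7: "Study centers will be added to the analysis of variance model for the primary endpoint". No other term is named in the visible text. Protocol 10.2.6 refers to a 95% confidence interval and leaves the detail to the SAP. The remainder of SAP 11.1 after the null hypothesis cannot be read.
- **Baseline score.** Protocol 4 has it recorded just before dosing, and Protocol 5.1 requires it to be at least 1.
- **Imputation.** After early rescue, SAP 9.1 says "the last pre-rescue assessments will be carried forward to the 2 hr assessment and to any post-rescue assessments". For a patient found not to have the disease, SAP 10.2 says "the outcome for the 2 hr assessment will be set to the baseline values".

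**The concern.** Taking a change from baseline subtracts the baseline score; it does not adjust for it. A patient who enters at 1 can improve by at most 1 unit, while one who enters higher can improve by more, so D2 is likely to depend on baseline severity. Leaving that variation in the error term widens the confidence interval that is compared with the margin. Put conditionally, a chance imbalance in baseline pruritus moves the unadjusted difference, and the visible plan has no pre-specified remedy for the primary result. These are two views of the same lost precision, not two harms.

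A separate matter is the exception in 9.4. It sets no threshold and no closed list, and it acts after arm differences have been seen. It applies only to the per-protocol set, so that supporting analysis could rest on a different model from the ITT analysis. If the two then disagreed, one could not tell an effect of the population from an effect of the model.

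**Working it through.** **Inputs from the documents.** 127 per arm (SAP 9.11: "the need for 127 subjects per treatment arm"), margin 0.50 (SAP 11.1), power 90% (SAP 6), two-sided 95% limits (SAP 9).

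**Assumptions.** One-sided 0.025 (to match the 95% interval), true difference zero, no dropout allowance. The SD and the alpha used for sizing are redacted, the pruritus scale is not visible, and no correlation is given. The figures below therefore illustrate the effect and do not estimate it.

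**1. SD implied by the plan's own sample size.** The figure of 127 cannot be reproduced independently, but it can be inverted:

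SD = 0.50 × √(127/2) / (1.960 + 1.282) = 0.50 × 7.969 / 3.242 = 1.229.

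The noncentral t gives 1.224. At one-sided 0.05 the normal formula gives about 1.36.

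**2. Change score against ANCOVA.** Let sb and sf be the SDs at baseline and 2 hours, and r their correlation.

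- Var(change) = sb² + sf² − 2·r·sb·sf
- Var(ANCOVA error) = sf²·(1 − r²)

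With assumed sb 0.6–0.7 and sf 0.8–1.0, the extremes are:

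| r | sb, sf | Var(change) | Var(ANCOVA) | Ratio |
|---|---|---|---|---|
| 0 | 0.7, 0.8 | 1.130 | 0.640 | 0.566 |
| 0.4 | 0.6, 1.0 | 0.880 | 0.840 | 0.955 |
| 0.5 | 0.7, 0.8 | 0.570 | 0.480 | 0.842 |
| 0.5 | 0.6, 1.0 | 0.760 | 0.750 | 0.987 |

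So the reduction in error variance runs from 43% down to about 1%.

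**3. Effect of the carry-forward rule.** A patient rescued before the first post-dose score has D2 set to zero whatever the baseline, which weakens the dependence. This was modelled with an assumed 0–3 scale, five mixes of baseline scores 1–3, and each unit of itch persisting with probability 0.2–0.4. The variance ratio was:

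- 0.43–0.79 with nobody carried forward at baseline
- 0.62–0.85 with 10% carried forward
- 0.73–0.89 with 20% carried forward

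**4. Power and interval width at 127 per arm.** Adjusted SD = 1.224 × √(1 − ρ²), where ρ is the correlation between baseline and D2. Half-width = t × SD × √(2/127).

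| ρ | Power | 95% CI half-width |
|---|---|---|
| 0 (unadjusted) | 90.0% | 0.303 |
| 0.2 | 91.1% | 0.297 |
| 0.3 | 92.5% | 0.289 |
| 0.4 | 94.3% | 0.277 |
| 0.5 | 96.3% | 0.262 |

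**5. Type I error.** The ordinal model of step 3 (baseline mix 0.2/0.4/0.4, persistence 0.3, no centre term) was simulated over 12,000 trials at a true difference of −0.50. The unadjusted test rejected in 0.024–0.028 of trials and the adjusted test in 0.025–0.027. Both are close to 0.025.

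**6. The same loss seen conditionally.** SE = 1.23 × √(2/127) = 0.154. With ρ = 0.3 and a baseline imbalance of two standard errors, the unadjusted difference shifts by 0.3 × 2 × 0.154 ≈ 0.093, which is 19% of the margin. The conditional error at the margin is P(Z > (1.96 × 0.154 ∓ 0.093) / (0.154 × √(1 − 0.09))). That is 7.7% when the imbalance favours cetirizine and 0.4% when it goes the other way.

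**The case against.** The strongest reply is that nothing here is invalid. The randomised comparison is unbiased, its error rate is nominal on average, and a wider interval makes non-inferiority harder to claim, so no false claim is favoured. A two-group calculation for sizing, followed by ANOVA with centre, is a coherent plan. All of that stands.

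The gain may also be negligible. The ordinal model used in step 5 has a D2 SD of only 0.86 to 0.98, not 1.22. At those SDs the unadjusted power is already 98.1% to 99.6%, and adjustment adds about 0.4 to 1.3 points. The SDs assumed in step 2 reach 1.22 only at one corner (r = 0, SDs 0.7 and 1.0). The large variance reductions and the 90% power case therefore hardly overlap, and the figures should not be combined. This also stands.

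The 7.7% needs an imbalance that only about 2.3% of randomisations would match or exceed in that direction, together with a true difference exactly at the margin. It describes a bad draw and is not an expected error rate.

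Two further points stand in part. SAP 7 places all non-inferiority analyses on ITT and gives the per-protocol set no decision rule, so the optional covariates there cannot alter the primary conclusion. They can only blur a supporting analysis. And the hidden part of 11.1 might name a baseline term. But 9.4 is fully visible and categorical, so such a term would contradict it and the two sections would have to be reconciled.

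**Conclusion.** The concern holds. On the visible text, the primary ITT analysis of D2 does not use the baseline pruritus score. The only route for covariates is chosen after seeing imbalance and is confined to the per-protocol set.

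The cost is precision, not validity. Its size cannot be fixed from the documents: at the SD implied by the sample size, the gain is about 1 to 6 points of power for a baseline/D2 correlation of 0.2 to 0.5; at an SD below 1 it is about a point or less. It rests on an assumed one-sided 0.025, a true difference of zero and the assumed correlations.

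The objection to the imbalance trigger needs no assumed figure. This is a change that should be made because it costs nothing, not because the trial would otherwise fail.

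**What to change.** Before unblinding, amend the SAP as follows:

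- State the primary model in 11.1 as an ANCOVA of D2 on treatment, baseline patient-rated pruritus and (pooled) centre. Compare the 95% confidence interval for the adjusted difference with −0.50.
- Use the same model in the ITT and per-protocol sets.
- Rewrite 9.4 to name baseline pruritus as the pre-specified covariate, and delete the imbalance-triggered option.
- Report the analysis without baseline adjustment as a sensitivity analysis.

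The cost is SAP wording only: the score is already collected on every patient before dosing, and the sample size need not change. The centre-pooling rule in 9.7 is incomplete as printed and has to be completed separately before the centre term is fully defined.

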### **9.5. Examination of Subgroups**

No subgroup analyses are planned.

### **9.6. Premature Discontinuation and Missing Data**

For any subject who withdraws prematurely from the study, all available data up to the time of discontinuation will be included in analyses.

### **9.7. Study Centers**

A total of 22 study centers will be used in this protocol. The likelihood that all centers enroll an equal number of subjects is small. No center will be allowed to enroll more than 20% of the entire study population (N=87). In the event there is a discrepancy of more than 10% between the largest enrolling center and smallest, centers will be pooled from the ranked extremes until the pooled centers are within of each other (e.g. the smallest center will be pooled with the largest, and so forth). Study centers will be added to the analysis of variance model for the primary endpoint. See [Section 10.1](#) for details of methods.

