  - *Time Spent at Treatment Center:* This will be defined as the difference between the time of treatment administration and of Readiness for Discharge. If a patient is admitted to hospital (not to go home), or stayed in ED observation overnight, the time to “Readiness for Discharge” is not recorded. These subjects will not be included in the summary analyses.

In addition, the following outcomes will be assessed by treatment as supportive information for the application:

- 1) *Pruritus Treatment Success:* A subject will be defined as having treatment success if the patient rated pruritus severity score at 2 hrs is at least 1 unit less than at baseline.
- 2) *Patient Rated Pruritus Severity Scores change at other time points:* The scores change/reduction from baseline at other assessment times (i.e.: 1 hr and at discharge)
- 3) *Sedation Score:* Subjects will be asked to rate their sedation at baseline, 1 hr, 2 hr and discharge.
- 4) *Physician Rated Extent of Urticaria/Erythema Scores:* Physicians will rate the percentage of body area affected and the intensity of redness on scales from 0 (none) to 3(severe) at baseline, 1 hr, 2 hr and discharge. The average of body area and intensity scores at each assessment time will be the Extent of Urticaria/Erythema score for that assessment time. This outcome will have the range from 0 to 3 with increments of 0.5 units.
- 5) *Proportion of Subjects Needing Rescue Medication:* A subject will be defined as needing rescue, if at any time after study drug and prior to readiness for discharge, the subject requires other medications for the symptoms of urticaria.
- 6) *Effectively Treated:* The investigator’s judgment of a subject’s effective treatment of symptoms (Yes/No).
- 7) *Symptom Recurrence:* Subjects will be followed up after 24 and 48 hours after discharge and asked if they have had any recurrence of symptoms since discharge.
- 8) *Need for Prescription Medications:* During the 24 and 48 hr follow up questions, subjects will be asked if they took any medications prescribed at discharge since discharge.
- 9) *Need for Additional Medications:* During the 24 and 48 hr follow up questions, subjects will be asked if they took any additional medications since discharge.
- 10) *Return to Normal Activity:* During the 24 and 48 hr follow up questions, subjects will be asked if they had returned to their normal activities.

See [Section 10.4](#) for detail on the specific analyses to be performed for each outcome.

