## 6. SAMPLE SIZE CONSIDERATIONS

Assuming the diphenhydramine treated group respond similar to ETtau-02 results, the common standard deviation is expected to be around CCI. A sample size of CCI subjects per arm (total CCI) is needed to provide 90% statistical power to determine that Cetirizine will be non-inferior to diphenhydramine. The sample size was calculated based on the CCI as the non-inferiority limit of the difference, using 1-sided test at alpha CCI. Sample size estimation was performed using CCI two-group t-test of equivalence in means (MTE0-1).

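### SAP 9.7 prints the 20% centre cap as N=87, which is 34% of the planned total; unless SAP 11.1 settles it, the size-based pooling rule also leaves the centre term of the primary model open

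*SAP*

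**What the plan says.** **Cap.** SAP 9.7 states "No center will be allowed to enroll more than 20% of the entire study population (N=87"). SAP sections 2 and 3 plan about 254 patients, and SAP 9.11 gives 127 per arm. The protocol summary plans about 256 patients at about 20 sites. Protocol 6.3 ships each site 13 blocks of four, enough for at most 52 patients.

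**Centres in the analysis.** SAP 9.7 also says:
- "A total of 22 study centers will be used in this protocol".
- Pooling is triggered as follows: "In the event there is a discrepancy of more than 10% between the largest enrolling center and smallest". Centres are then combined from the two ends of the size ranking, and the example given is that "the smallest center will be pooled with the largest, and so forth".
- After any pooling, centre becomes a term in the main model: "Study centers will be added to the analysis of variance model for the primary endpoint".

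Protocol 6.3 has a separate randomisation list for each site, in blocks of four.

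**Pointers.** SAP 9.7 sends the reader to Section 10.1 for methods. SAP 9.2 does the same ("Details of the methods to be used are provided in" Section 10.1). SAP section 2 refers to Section 10.4 "for detail on the specific analyses to be performed for each outcome". In the SAP as it stands, 10.1 is Subject Accountability and 10.4 describes the study population. The primary analysis is in 11.1 and the efficacy analyses are in Section 11.

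**The concern.** The printed number and the stated percentage cannot both be right. A site or monitor working from the number would apply a limit about 70% higher than the rule in words (87/50.8 = 1.71).

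The pooling rule is a different matter. The design balances treatment within site, so site is the natural grouping for the analysis. Section 9.7 instead forms groups by matching large centres with small ones, which share nothing but their place in the ranking. Two parts of the rule are open in the visible text:
- whether the 10% is relative to a centre's size or a share of total enrolment;
- whether the ranking is redone after each merge or whole rounds of pairs are formed.

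The number of centre levels in the primary model can depend on the answers. A choice of that kind should not be left until treatment codes are known.

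**Working it through.** **1. The cap**

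Inputs: 20% and N=87 (SAP 9.7); 254 (SAP sections 2 and 3; 2 × 127 from 9.11); 256 (protocol summary); 52 per site (Protocol 6.3).

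| Reading | Calculation | Result |
|---|---|---|
| 20% of the SAP total | 0.20 × 254 | 50.8, so at most 50 (50/254 = 19.7%) |
| 20% of the protocol total | 0.20 × 256 | 51.2, so at most 51 (51/256 = 19.9%) |
| 20% of one arm | 0.20 × 127 | 25.4 |
| 87 as a share | 87/254; 87/256 | 34.3%; 34.0% |
| Total that would make 87 right | 87/0.20 | 435, found nowhere in the documents |
| 87 as the population | 0.20 × 87 | 17.4, and 87 contradicts 254 and 256 |
| Drug supply per site | 52/254; 52/256 | 20.5%; 20.3% |

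No reading reproduces 87. The supply figure is consistent with a cap near 51.

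**2. The trigger**

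This step does not depend on the stopping tolerance. The average centre has 254/22 = 11.5 patients.
- Relative to the larger centre: 12 against 10 is (12 − 10)/12 = 16.7%, so a gap of two patients can start pooling.
- As a share of 254: 25/254 = 9.8% does not start pooling and 26/254 = 10.2% does, so the gap must be at least 26 patients.

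**3. What the base does to the centre term**

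The documents give no centre sizes. Three assumed sets are used, each with 22 centres, sum 254 and none above 50:
- A: 48, 34, 27, 22, 18, 15, 13, 11, 10, 9, 8, 7, 6, 5, 5, 4, 4, 3, 2, 1, 1, 1
- B: 26, 22, 20, 18, 17, 16, 15, 14, 13, 12, 12, 11, 10, 9, 8, 7, 6, 5, 5, 4, 3, 1
- C: 40, 22, 20, 18, 16, 15, 14, 13, 12, 11, 10, 10, 9, 8, 8, 7, 6, 5, 4, 3, 2, 1

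Pooling stops when the spread is within 10%, which is an assumption. Pairing in rounds means smallest with largest, second smallest with second largest, and so on, repeated until the stop is met.

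| Set | 10% relative, rounds | 10% of 254, rounds | Re-ranked after each merge |
|---|---|---|---|
| A | 3 levels | 3 levels | 1 level, either base |
| B | 1 level | 22 levels (not triggered) | 1 level (relative); 22 (of 254) |
| C | 3 levels | 11 levels | 1 level, either base |

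One level means that there is no centre term. In set C, for example, the first round gives 11 pools of 20 to 41 patients. That spread of 21 is within 25.4 (10% of 254) but not within 10% of 41, so only the relative reading goes on, ending at 3 pools of 82 to 86.

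**4. Precision**

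Simulation: 20,000 trials per cell, blocks of four within site, least squares with treatment plus group, margin 0.50 (SAP 11.1). The SD and alpha are redacted. A total SD of 1.22 was back-calculated from 127 per arm, 90% power, true difference 0 and an assumed one-sided alpha of 0.025. The width ratios do not depend on that SD. The between-site share of variance is also assumed. The table gives the 95% CI width compared with a fixed site term, over sets A to C.

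| Levels | Share 0 | Share 0.06 | Share 0.20 |
|---|---|---|---|
| 1 | 0.6–1.1% narrower | 1.7–2.4% wider | 9.5–10.5% wider |
| 3 | 0.6–1.0% narrower | 1.2–2.1% wider | 7.6–9.2% wider |
| 11 | 0.4–0.9% narrower | 0.2% narrower to 0.7% wider | 1.9–4.1% wider |

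Check for one level, before the cost of the site term: 1/√(1 − 0.06) = 1.031 and 1/√(1 − 0.20) = 1.118.

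One-sided type I error was 0.024–0.027 with site and 0.015–0.027 pooled (Monte Carlo SE 0.0011). Power at share 0.20 was 95% with site and 92% with one pool.

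**The case against.** The strongest reply is that little here affects the result. The cap is given correctly in words, 87 feeds no visible analysis, and drug supply was planned near 20%. That stands, and it makes the cap an editorial correction. The supply figure is supporting evidence only, since Protocol 6.3 does not rule out resupply.

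On pooling, a reader might infer that the pairing order is unspecified. It is not: 9.7 says centres are taken from the ranked extremes, smallest with largest. Only the base and the re-ranking are open. The tolerance at which pooling stops falls in a gap in the available text and is not counted as missing. SAP 11.1 is visible only as far as the null hypothesis, so its remainder may define the centre term. The pooling point is therefore conditional.

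A reader might also infer that one data set could give 1, 3, 11 or 22 levels. None of the three sets does so, and part of any wider spread would come from varying the unseen tolerance. With the tolerance held at 10%, the base makes no difference in set A.

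Finally, a fixed site term is not free. If sites do not differ, power falls slightly below 90%, and single-patient sites add nothing to the treatment contrast. That is a fair cost, and it is small.

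**Conclusion.** The cap is wrong as printed: 87 against 50 or 51. This rests on the documents' own totals and needs no assumption.

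The pooling point holds in a narrower, conditional form. If 11.1 does not settle the term, the visible rule leaves the primary model open, and in two of three assumed size sets the base of the 10% alone changes the number of levels. Against a fixed site term, one pool makes the interval anywhere from about 1% narrower to about 10% wider as the assumed between-site share goes from 0 to 0.20. The documents give no value for that share.

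It may be tempting to conclude that pooling biases the comparison, makes a false claim of non-inferiority more likely, or leaves the trial underpowered. The material does not support this. The simulated type I error is nominal or conservative. The sample size came from a "two-group t-test of equivalence in means (MTE0-1"), with no centre term mentioned, so pooling does not take power below plan.

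Nor do the wrong pointers show that methods are missing. They fit a single renumbering slip in which Section 10 became Section 11.

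**What to change.** 1. In SAP 9.7, replace 87 with 50 (if the total is 254) or 51 (if 256). If 87 was meant as the study population, correct that total instead.
2. Unless 11.1 already fixes the centre term, use the actual randomisation site as a fixed effect in the primary analysis of variance, without size-based pooling, and settle this before unblinding. If the sponsor keeps pooling, state the base of the 10% and whether pools are re-ranked after each merge.
3. Point the Section 10.1 references in 9.2 and 9.7 to 11.1, and the Section 10.4 reference in section 2 to Section 11.

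Cost: SAP wording only, since site is already recorded. A site term for 22 centres uses 22 − 1 = 21 degrees of freedom. If sites do not differ, the interval is about 0.6–1.1% wider and simulated power is 89.4–89.8% instead of 90.1–90.2%, under the assumed SD and alpha. Those figures already allow for single-patient sites.
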